## 10.4 Clinical Follow-up occurs at Day 28 and Day 56 after registration unless patient withdrawal has occurred.

If the patient has achieved clinical improvement, the patient will be observed at 56 days, from time of registration.

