## 10.3 Off protocol treatment

Follow the table below for patient follow-up after patient goes off protocol treatment.

CFU=Clinical Follow-Up

Reason Off Treatment	Go to CFU, or end follow-up
Treatment (Intervention) Completed Per Protocol Criteria	CFU
Patient Withdrawal/Refusal After Beginning Protocol Therapy (Intervention)	CFU
Adverse Events/Side Effects/Complications	CFU
Clinical deterioration During Active Treatment (Intervention)	CFU
Alternative Therapy	No follow-up
Patient Off-Treatment (Intervention) For Other Complicating Disease	CFU
Death On Study	No follow-up
Other	CFU
Clinical deterioration Before Active Treatment (Intervention)	No follow-up
Patient Withdrawal/Refusal Prior To Beginning Protocol Therapy (Intervention)	No follow-up

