#### 13.4 Planned Analyses

##### Primary Analysis

Frequency distributions and chi-square tests will be used to screen for major imbalances in the two randomization groups for qualitative variables; graphical displays including box plots and summary statistics (e.g., mean, median, standard deviation, ranges, etc.) will be used for quantitative variables with t-tests (after appropriate transformations if necessary to meet the assumptions of the methods).

The primary outcome will include the number of patients who are alive AND free from respiratory failure at Day 28 divided by the total number of patients in each arm. This endpoint will be analyzed in a binary fashion using properties of the binomial distribution and will be compared between randomized arms by the use of independent samples Z-test for proportions and a 95% confidence interval will be constructed for the difference between arms. Proportions will also be compared using Cochran-Mantel-Haenszel tests, including the stratification factors of age and baseline disease severity. Multivariable logistic regression models will be used to assess the influence of treatment while controlling for covariates of interest (gender, symptom onset, comorbidities) along with stratification factors. Primary analysis for this efficacy outcome will include all participants who are randomized and received at least 1 dose of study treatment. Participants will be analyzed according to the treatment to which they were randomized.

Efforts to minimize loss to-follow-up will be considerable. However, small amounts of missing data may occur. In such cases, participants without Day 28 outcome data will be excluded from the analysis. Sensitivity analyses will evaluate the impact of making different assumptions about the missing observations.

**Interim analyses:** Two interim analyses will be conducted after 25% and 50% of patients have completed the 28 day study period. The interim analysis will include the below stopping rules for efficacy and futility based on a Lan-DeMets spending function with O'Brien-Fleming boundaries. Occurrence of adverse events will also be evaluated at the interim analysis.

Accrual	Control arm (#)	Camostat arm (#)	Total number (#)	Efficacy boundary (Z scale)	Alpha spent	Futility boundary (Z scale)	Beta spent
25%	33	33	66	+/- 4.33	0.001	+/- 0.007	0.002
50%	66	66	132	+/- 2.96	0.003	+/- 0.34	0.04
100%	132	132	264	+/- 1.97	0.05	+/- 1.97	0.20

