#### Missing Data Considerations

All efforts will be made to minimize the occurrence of missing data. Subjects who discontinue treatment in either arm will be encouraged to remain in the study and to continue with follow-up visits for key outcomes at Day 28 and 56.

For time to event outcomes, subjects who are lost to follow-up or withdrawal from the study prior to Day 28 and prior to observing/experiencing the event will be censored at the time of their last observed assessment.

For duration of non-invasive ventilation/high-flow oxygen, ventilation/ECMO or supplemental oxygen, subjects will be considered to have the event of interest until Day

28 if they have the event of interest at their last follow-up assessment day before Day 28 in the case of lost to follow-up or patient withdrawal. Likewise, if they do not have the event of interest at their last follow-up assessment, they will be considered to not have this event through Day 28.

If the subject is discharged and no further hospitalization data are available, then the subject will be assumed to not have been readmitted to the hospital.

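### Sections 10.3 and 10.4 conflict on Day 28 follow-up for patients who withdraw from or refuse study drug after starting it, and Section 13.4 excludes any of them left without a Day 28 outcome

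*Combined protocol and SAP*

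**What the plan says.** Four places bear on this point.

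- **Section 10.3, off-treatment table.** The row "Patient Withdrawal/Refusal After Beginning Protocol Therapy (Intervention" leads to clinical follow-up. The matching row for withdrawal before therapy, "Patient Withdrawal/Refusal Prior To Beginning Protocol Therapy (Intervention", leads to no follow-up. Adverse events, deterioration during treatment, other complicating disease and other reasons all lead to clinical follow-up. "Alternative Therapy" leads to no follow-up.
- **Section 10.4.** Follow-up takes place at Days 28 and 56, counted from registration, "unless patient withdrawal has occurred". The term is not defined there.
- **Section 13.5, Missing Data Considerations.** "Subjects who discontinue treatment in either arm will be encouraged to remain in the study and to continue with follow-up visits for key outcomes" at Days 28 and 56. The next paragraph speaks separately of people who withdraw from the study.
- **Section 13.4, Primary Analysis.** The analysis covers everyone randomized who took at least one dose, but "participants without Day 28 outcome data will be excluded from the analysis". Sensitivity analyses for the missing observations are promised, without stated assumptions.

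**The concern.** For one group of patients, one section orders the Day 28 visit and the next appears to cancel it. Section 10.3 has just used patient withdrawal as a reason for going off treatment, so a coordinator reading on to 10.4 can fairly take the words in the same sense. Two sites could handle the same patient in opposite ways, each with a section to point to.

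Day 28 status is the primary outcome. If it is not collected, the patient leaves the primary analysis under 13.4, although 13.3.1 sets the denominator as all patients enrolled in the arm. Sensitivity analyses can bracket the missing values but cannot recover a status that was obtainable and never sought. Refusal of further drug may be related to how the patient is doing. That is plausible, but the documents do not establish it.

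**Working it through.** **1. The text, case by case.** Take a patient who started therapy and then stopped.

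| Reason off treatment | Section 10.3 | Section 10.4, withdrawal = stopping drug | Section 10.4, withdrawal = leaving the study |
|---|---|---|---|
| Withdrawal or refusal, still willing to be contacted | follow-up | no follow-up: **conflict** | follow-up |
| Adverse event, deterioration, complicating disease, other | follow-up | follow-up | follow-up |
| Alternative therapy | no follow-up | not addressed | not addressed |

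The conflict is confined to the first row and depends on the reading of one undefined term. The third row is a separate mismatch: 10.3 ends follow-up, while the missing-data text says "Subjects who discontinue treatment in either arm will be encouraged to remain in the study" and makes no exception for alternative therapy.

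**2. The plan's own figure.** Section 13.6 gives 132 per arm, 80% against 92%, two-sided 0.05, Z-test with unpooled variance, 80% power. Section 13.4 gives a final boundary of 1.97.

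SE = √[(0.80×0.20 + 0.92×0.08)/132] = √(0.2336/132) = 0.04207

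Power = Φ(0.12/0.04207 − 1.97) = Φ(0.883) = 81.1% (81.4% with 1.96)

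The stated 80% is reproduced. The 264 contains no allowance for dropout.

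**3. Power if patients are lost by this route.** The loss rates are assumptions. The formula is as above, with n = 132 × (1 − loss), as a single look at the final boundary that ignores the interim analyses.

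| Assumed loss per arm | n per arm | 0.12/SE | Power at 1.97 | Power at 1.96 |
|---|---|---|---|---|
| 0% | 132 | 2.853 | 81.1% | 81.4% |
| 5% | 125.4 | 2.780 | 79.1% | 79.4% |
| 10% | 118.8 | 2.706 | 76.9% | 77.2% |

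**4. Bias when there is no true effect.** Assume 80% success in both arms. If a fraction w of an arm is lost and has success rate q, the rate among those remaining is (0.80 − w·q)/(1 − w). All values of w and q are assumptions.

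- Loss of 8 of 132 on camostat and 3 of 132 on placebo, q = 50% in both. Expected successes are 132 × 0.80 = 105.6 per arm. Camostat: (105.6 − 4)/124 = 81.9%. Placebo: (105.6 − 1.5)/129 = 80.7%. The spurious difference is 1.2 points.
- Loss of 10% on camostat only, q = 50%: (0.80 − 0.05)/0.90 = 83.3%, a spurious 3.3 points.
- The same loss with q = 30%: (0.80 − 0.03)/0.90 = 85.6%, a spurious 5.6 points.
- The same loss with q = 80%: (0.80 − 0.08)/0.90 = 80.0%, no bias.

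For scale, the standard error of the difference with 80% in both arms is √(2 × 0.16/132) = 4.9 points. The first example is therefore about a quarter of one standard error, against a design effect of 12 points.

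**The case against.** The strongest reply is that 10.4 means leaving the study. The time-to-death definition in 13.3.2 and the missing-data text use withdrawal in that sense, and the latter treats stopping treatment as something different. On that reading 10.4 says only that people who have left are not followed, and nothing conflicts. The 10.3 table is also introduced as the instruction to use once a patient goes off treatment. This reading is reasonable and probably what was meant. But Section 10 does not state it, and sites work from Section 10.

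The second reply is that the reasons most likely to be related to outcome are covered elsewhere. Adverse events and deterioration have their own rows leading to follow-up, Section 10.2 repeats this for deterioration, and Section 10.6 does the same for major violations who stop treatment. Section 8.5.2.3.1 also requires deaths within 56 days of registration to be submitted. All of this stands. A reader might infer that 10.4 costs every patient who stops treatment their primary outcome, and the documents do not support that. What stays exposed is the patient recorded as a withdrawal or refusal who can still be contacted. For that patient, death reporting does not show whether a survivor is free of respiratory failure.

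Third, the effect is small under moderate assumptions, and sensitivity analyses are planned. That is correct, and it limits the weight of the point without removing the contradiction.

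**Conclusion.** The point holds in a narrow form. Sections 10.3 and 10.4, read literally, give opposite instructions for patients who withdraw from or refuse study drug after starting it. Where a site follows 10.4 and no Day 28 status is obtained, 13.4 excludes a patient whom 10.3 and the missing-data text mean to keep.

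The loss is conditional on how sites read an undefined term. The size is unknown because no withdrawal rate is given. Under assumed losses of 5% or 10% per arm by this route alone, power goes from about 81% to about 79% or 77%. With no true effect, bias in the treatment difference arises only if withdrawal is related to outcome and its pattern differs between arms. A reader might infer that biased results are to be expected, but the documents offer no evidence for either condition. Nor do they keep everyone who stops treatment in follow-up: the missing-data text only encourages it, and the alternative-therapy row of 10.3 ends it outright.

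This is an inconsistency of wording that touches the primary outcome. It is worth correcting because the loss is avoidable.

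**What to change.** - Reword the exception in Section 10.4 to: *unless the patient has withdrawn consent for follow-up*.
- Add a sentence saying that patients who stop study drug only are still assessed, remotely if needed, for ordinal score and vital status at Days 28 and 56.
- In the same amendment, reconcile the alternative-therapy row of the 10.3 table with the missing-data text, which encourages all subjects who discontinue treatment to continue Day 28 and Day 56 follow-up. The 10.4 edit alone would not settle this.

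The cost is a short text amendment and a note to sites. The Day 28 and Day 56 assessments are already scheduled, and footnote o of the Section 4.0 test schedule already allows remote monitoring after Day 1. The sample size, boundaries and stated power do not change.

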## 10.5 Ineligible

A patient is deemed *ineligible* if after registration, it is determined that at the time of registration, the patient did not satisfy each and every eligibility criteria for study entry.

- If the patient received treatment, the patient may continue treatment at the discretion of the physician as long as there are not safety concerns. The patient will continue in the Active Monitoring/Treatment phase of the study, as per section 4.0 of the protocol.
- If the patient never received treatment, on-study material must be submitted. Clinical

Follow-up will be required per Section 4.0 of the protocol.

#### 10.6 Major violation

A patient is deemed a *major violation*, if protocol requirements regarding treatment of the initial therapy are severely violated that evaluability for primary end point is questionable. If the patient received treatment, the patient may continue treatment at the discretion of the physician as long as there are no safety concerns. The patient will continue in the Active Monitoring/Treatment phase of the study, as per section 4.0 of the protocol, and all data submission should continue per protocol. If the patient does not continue with treatment, the patient will go off treatment and be followed in Clinical Follow-up.

#### 10.7 Cancel

A patient is deemed a *cancel* if he/she is removed from the study for any reason before any study treatment is given. On-study material and the Off Treatment form must be submitted. No further data submission is necessary.

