#### 6.1.7 Treatment

Treatment cannot begin prior to registration and must begin  $\leq$  5 days after registration.

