8.5.2.3 Grade 5 AEs (Deaths)

8.5.2.3.1 Any death within 56 days after registration on the trial must be submitted as a Grade 5 AE, with a CTCAE type and attribution assigned.

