#### 13.3.2 Secondary Endpoints

1. Proportion of patients alive AND free of ventilator use or ECMO at Day 28: The proportion will be evaluated based on the number of patients who are alive AND free of ventilator use or ECMO (clinical status score of 5 or less) at Day 28 after study entry divided by the number of total patients enrolled for each treatment arm.

2. Time to death: Time to death will be measured as the number of days from the date of randomization/study entry until death date. Deaths due to any cause will be considered an

event. All-cause mortality rate at 28 and 56 days after study entry will be evaluated. If the patient is lost to follow-up or withdraws from the study early, or doesn't experience a death event, they will be censored at Day 28.

**3. Time to clinical improvement:** Clinical improvement will be defined as a 2 or more point decrease on the WHO ordinal scale (see Section 12.0). Time to clinical improvement will be calculated as the number of days from study entry until the earliest date of clinical improvement as defined above. The number of patients who achieve clinical improvement by Day 14 and 28 will be evaluated. In addition, time to clinical improvement will also be assessed.

**4. Clinical status at Days 14 and 28:** Evaluation of the distribution of clinical status scores by the ordinal scale will be done at days 14 and 28.

**5. Length of Hospitalization Stay:** This will be defined as the time from randomization/study entry until the time of hospital discharge. Time in the ICU will be described in number of days spent receiving ICU care, if applicable.

**6. Duration of Mechanical ventilation / ECMO:** Ventilator / ECMO days will be defined as the number of days where the clinical status score is equal to 6 or 7 for those subjects who have a baseline score of 6-7 at study entry. Total number of days will be the sum of all reported days, regardless of whether the days occur consecutively or in disjoint intervals.

**7. Duration of non-invasive ventilation / high-flow oxygen:** Non-invasive ventilation / high-flow oxygen days will be defined as the number of days where the clinical status score is equal to 5 for those with a baseline score of 5 at study entry. Total number of days will be the sum of all reported days, regardless of whether the days occur consecutively or in disjoint intervals.

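### Sections 10.3 and 10.7 stop outcome follow-up for randomised patients who are never dosed, in conflict with the 56-day death-reporting rule in 8.5.2.3.1 and with the enrolled denominators in 13.3

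*Combined protocol and SAP*

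**What the plan says.** **Rules that stop follow-up.** Section 10.7 defines a cancel as a patient "removed from the study for any reason before any study treatment is given". For such a patient: "On-study material and the Off Treatment form must be submitted. No further data submission is necessary". The table in 10.3 assigns no follow-up to two pre-dose reasons: "Clinical deterioration Before Active Treatment (Intervention") and "Patient Withdrawal/Refusal Prior To Beginning Protocol Therapy (Intervention").

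**Rules that require data.** Section 8.5.2.3.1 states: "Any death within 56 days after registration on the trial must be submitted as a Grade 5 AE". It sets no dosing condition. Section 10.5, which covers only patients found ineligible after registration, says of those never treated that Clinical "Follow-up will be required per Section 4.0 of the protocol".

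**The interval.** Section 6.1.7: "Treatment cannot begin prior to registration and must begin" no more than 5 days after registration.

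**The analysis.** Sections 13.3.1 and 13.3.2 (item 1) divide by everyone enrolled in the arm. For mortality, 13.3.2 (item 2) says: "Time to death will be measured as the number of days from the date of randomization/study entry until death date", counting death from any cause. Section 13.4 restricts the primary analysis to randomised patients with at least one dose. Section 13.1 uses the same restriction and adds eligibility. Section 13.2 assumes 56 days of follow-up for all patients.

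**The concern.** A site with a randomised but undosed patient is told in one place to stop and in another to report any death to Day 56. The protocol does not say which rule prevails. A site that follows 10.3 or 10.7 has no scheduled contact at which it would learn of a later death, or of the patient's respiratory status at Day 28.

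At stake is whether the trial can describe what happened to everyone it randomised. Receiving a first dose is an event after randomisation, and the protocol itself foresees deterioration before it. If outcomes of undosed patients are not collected, nobody can later check whether leaving them out mattered. The endpoint definitions that count all enrolled patients also cannot be applied as written.

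**Working it through.** **Step 1. The rules side by side, for a randomised patient who has received no study drug.**

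| Patient | Stops follow-up | Requires data |
|---|---|---|
| Eligible, deteriorates before dosing | 10.3; also 10.7 if removed | 8.5.2.3.1 (death to Day 56) |
| Eligible, withdraws before dosing | 10.3; also 10.7 if removed | 8.5.2.3.1 (death to Day 56) |
| Found ineligible, never treated | 10.7, if treated as removed | 10.5 (Clinical Follow-up) and 8.5.2.3.1 |

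The first two rows conflict directly over deaths. In the third row the conflict is softer, because 10.5 can be read as the specific rule that keeps these patients in the study, so that they never become cancels. In the first two rows no section requires a Day 28 ordinal score.

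The missing-data text in 13.5 does not close the gap. It encourages patients who discontinue treatment to stay for Day 28 and Day 56, but does not mention those who never start.

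**Step 2. The plan's own figure.** Inputs from 13.6: 132 per arm, 80% versus 92%, two-sided 0.05, Z-test with unpooled variance.

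- Standard error = √[(0.80 × 0.20 + 0.92 × 0.08)/132] = √(0.2336/132) = 0.0421.
- Power = Φ(0.12/0.0421 − 1.96) = 0.81.

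The stated 80% power is reproduced. Section 13.6 makes no allowance for undosed patients.

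**Step 3. Scale, under an assumption.** The documents give no pre-dose loss rate. Assume 2%, 5% or 10% undosed, equal in the two arms, and the planned 92% and 80% among the dosed. Let m be the undosed and n = 132 − m the dosed patients per arm. With undosed outcomes unknown, the all-randomised difference lies between these extremes:

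- lower: (0.92n − 0.80n − m)/132, with every undosed camostat patient failing and every undosed control patient succeeding;
- upper: (0.92n + m − 0.80n)/132, the reverse.

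| Assumed undosed | m | n | 0.12n | Lower | Upper | Dosed-only power |
|---|---|---|---|---|---|---|
| 2% | 3 | 129 | 15.48 | 12.48/132 = 9.5 points | 18.48/132 = 14.0 points | 0.805 |
| 5% | 7 | 125 | 15.00 | 8.00/132 = 6.1 points | 22.00/132 = 16.7 points | 0.793 |
| 10% | 13 | 119 | 14.28 | 1.28/132 = 1.0 point | 27.28/132 = 20.7 points | 0.773 |

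These are logical limits, not likely values. They show what could not be ruled out from the data if follow-up stopped. The dosed-only analysis itself loses little power.

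**The case against.** The strongest defence is that the dosed-patient population is a deliberate choice in 13.1 and 13.4. Assignment is double-blind, so the reasons for not being dosed should not depend on arm. The planned primary result does not use these patients and would not change. All of that stands. It does not settle which instruction a site should follow, supply the enrolled denominators, or complete mortality counted from randomisation. Blinding removes expected imbalance but not chance imbalance.

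Several stronger readings are tempting, and the documents do not support them:

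- *All data collection ends.* On-study material and the Off Treatment form are still required, and 10.3 provides a specific reason for deterioration before treatment. What is lost is later outcome status.
- *Deaths before dosing are not captured.* Section 8.5.2.3.1 requires them. They are lost only if a site lets 10.3 or 10.7 override it. These are hospital inpatients, so many such deaths may be known anyway.
- *No intention-to-treat analysis can be done.* Assignment is known for everyone. Bounds or imputation remain possible; an analysis on complete observed outcomes does not.
- *Section 10.5 is a general rule for undosed patients.* It covers ineligible patients only.
- *The dosed set must do better than the randomised population.* Some undosed patients may have improved and gone home, so the direction is unproven.
- *Undosed patients are not replaced.* The documents do not say either way.

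The 5 days in 6.1.7 is also a ceiling. No typical interval is given, and 6.1.8 says kits are on site without saying whether they hold drug or specimen supplies.

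**Conclusion.** The point holds as a conflict between data-collection rules with a modest analytic consequence. Sections 10.3 and 10.7, followed as written, leave Day 28 status, and possibly deaths to Day 56, unobserved for randomised patients whom 13.3.1 and 13.3.2 count in the denominator. They conflict with 8.5.2.3.1 and sit poorly with 10.5.

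The size is unknown and may be small. The 6-to-17-point range rests on an assumed 5% undosed in each arm and on the planned 12-point difference among the dosed. It is not an estimate of bias, and nothing here shows that the dosed-patient primary comparison is biased. The case for changing the plan is that the repair is cheap and that outcomes not collected at the time may be hard to recover later.

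**What to change.** 1. Reconcile the two pre-treatment rows of 10.3, and 10.7, with 8.5.2.3.1 and 10.5. Unless consent for data is withdrawn, obtain the Day 28 ordinal score and the Day 28 and Day 56 vital status of every randomised patient, by chart review or telephone. Notes l and o of the test schedule already accept remote contact for discharged patients.
2. Keep the dosed-patient analysis of 13.4 as primary, and align the population in 13.1 and the denominators in 13.3.1 and 13.3.2 with it.
3. Add an all-randomised sensitivity analysis of the primary endpoint and of mortality, with pre-dose losses tabulated by arm and reason.

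The cost is wording changes, a few remote contacts for undosed patients, one sensitivity analysis and one table. The all-randomised estimate will be slightly diluted, which is acceptable for a sensitivity analysis.
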